## [Rationale]

Among the efficacy-related items, (1) is to supplement the primary endpoint, (2) - (4) are typical non-remission efficacy endpoints. The composite outcome was included to assess the efficacy-safety balance. (5), (6), (7), (8) are indices of the disease activity, irreversible damage caused by the disease, patient QOL [18], and overall patient evaluation, respectively. (9) is considered necessary to prove the hypothesis of this study.

Among the safety-related items, we think that (1) is required for general safety evaluation of a clinical study. (2) - (5) are items to reflect adverse effects of glucocorticoids, which represent a major focus of this

study.			

## 9.3 Exploratory endpoints

- ① Immunoglobulin concentration
- ② Whole blood B cell count
- ③ Changes in MPO-/PR3-ANCA values associated with treatment, treatment responses, and relapses

Endpoint	Event (whichever is earlier if more than one)	Date censored	Competing risk
Time to B cell recovery	B cell recovery	The last day of confirmed	Death
		absence of B cell recovery	

## [Rationale]

We think that these exploratory endpoints are candidate biomarkers, of which (1) serves as an index of side effects, and (2) and (3) serve as efficacy indices.

## **10. Statistical Matters**

## **10.1 Analysis sets**

## 10.1.1 Full Analysis Set (FAS)

The full analysis set (FAS) comprises all subjects enrolled in this study that received at least one dose of a study medication after randomization and visited hospital at least once during the treatment period, from which efficacy data are available. However, subjects are excluded if baseline data cannot be obtained. Subjects are also excluded if there is any serious protocol violation (e.g., consent has not been obtained, patient enrolled outside the contract period).

## 10.1.2 Per Protocol Set (PPS)

This comprises the remainder of FAS after excluding subjects with any of the following major violations of provisions of the protocol, such as study procedures and concomitant medications.

Violation of inclusion criteria

Violation of exclusion criteria

Less than 75% adherence to the study medication

#### 10.1.3 Safety analysis set

All subjects enrolled in this trial who received at least one dose of a trial medication will be included in analyses. The subjects are divided into groups according to the trial medication that they actually received.

#### 10.2 Target sample size and underlying rationale

Up to 140 cases

#### [Rationale]

To demonstrate the non-inferiority in remission induction rate, the necessary number of cases calculated with the following conditions is 63 in each arm:

 $\alpha = 0.025$  (one-tailed),  $1 - \beta = 0.8$ 

(1)Remission induction rate with rituximab + high-dose glucocorticoids = 0.80

(2)Remission induction rate with rituximab + low-dose glucocorticoids = 0.80

Non-inferiority margin=-0.2

Allocation ratio, 1:1.

With a predicted withdrawal rate of 10%, the target sample size was set as 70 in each arm, a total of 140 cases. The induction rates (1) and (2) are based on RITUXVAS study [8] and the Cambridge University cohort, respectively [14].

## 10.3 Case handling

As a general rule, the coordinating investigator determines how to handle registered cases. When a new problem has arisen, the statistical analysis supervisor or the Efficacy and Safety Assessment Committee discuss and decide how to handle it as needed.

## **10.4 Data handling**

During data tabulation and analysis, the coordinating investigator determines how to handle the data as a general rule. However, when a question has arisen, the coordinating investigator consults the statistical analysis supervisor or the Efficacy and Safety Assessment Committee before making a decision.

Missing laboratory test data will be supplemented as needed. For more information, see the Statistical Analysis Plan.

#### 10.5 Statistical analysis items and analytical plan

Efficacy and safety analyses including the primary endpoint will be conducted after all subjects have completed the study medication in the remission induction phase and the data have been fixed (data at 6

- 41 -

months). Thereafter, the data for the remission maintenance phase (at 24 months) are also analyzed to assess the efficacy and safety in a longer term. In all efficacy assessments, the analysis in the full analysis set (FAS) is the primary analysis, and the analysis in the Per Protocol Set (PPS) is done for the purpose of reference. Safety Analysis Set will be used for safety-related analyses.

Major analytical methods are described below. Further details of analyses will be described in the Statistical Analysis Plan, which will be prepared before the data fixation.

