## 9.2 Secondary endpoints

## [Efficacy]

- 1 Time to remission
- ② Overall survival period, relapse-free period, time to ESRD, time to the first serious adverse event These endpoints are defined as a length of time from the time of randomization to the occurrence of respective events, and patients who did not experience the event will be counted as censored. Definitions of event and date censored for each endpoint are shown in a table below.

Endpoint	Event (whichever is	Date censored	Competing risk
	earlier if more than one)		
Time to remission	Remission	The last day of confirmed	Death
		absence of remission	
Overall survival period	Any death	The last day of confirmed	None
		survival	
Relapse-free survival	Any death, relapse	The last day of confirmed	None
period		absence of relapse	
Time to ESRD	ESRD	The last day of confirmed	Death

		absence of ESRD	
Time to the first serious	First serious adverse event	The last day of confirmed	None
adverse event	(including death and	absence of serious adverse	
	hospitalization)	event	

- ③ The proportion of death, relapse, ESRD, or serious adverse events, and proportion of a composite outcome thereof (at 6 and 24 months; \*at 6 months, proportions of death, ESRD, and serious adverse events only)
- ④ Proportions of minor and major relapses (at 24 months)
- (5) The proportion of participants who achieved remission and glucocorticoid cessation
- (6) Assessment of disease activity using BVAS ver3 (at 6 and 24 months)
- ⑦ Irreversible damage measured using VDI (at 24 months)
- 8 Evaluation of health-related QOL using SF-36 (at 6 and 24 months)
- 9 Patient general assessment with a VAS (at 6 and 24 months)
- (1) Cumulative glucocorticoid dose (at 6 and 24 months)

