## [Safety]

- ① The number of occurrence and proportion of adverse events and serious adverse events that occurred (at 6 and 24 months)
- 2 Proportions of new-onset diabetes, hypertension, and dyslipidemia requiring treatment (at 6 and 24 months)
- ③ Proportion of sleep disorder requiring treatment (at 6 and 24 months)
- ④ Proportion of pathological fractures and bone density of the lumbar spine (at 24 months)
- (5) The number of occurrence and proportion of infections (intravenous or oral antibiotics are used) (at 6 and 24 months)

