#### 10.5.2.2 Secondary efficacy endpoint analyses

The secondary efficacy endpoint data will be analyzed for the purpose of discussions that supplement the results from the primary analyses. The adjustment of multiplicity will not be performed in the analyses on the secondary efficacy endpoints. The significance level in the hypothesis test will be 5% (two-sided), and confidence intervals to be calculated are two-tailed 95% confidence intervals.

Among the secondary endpoints, duration of remission, overall survival, relapse-free survival, time to ESRD, and time to the first serious adverse event are measured from the time of randomization as the starting point, and survival time analysis and competing risk analysis will be performed on lengths of time to respective events.

For proportions of death, relapse, ESRD, and serious adverse events, and proportions of the composite outcome thereof, proportions of occurrence of events at each time point and two-tailed 95% confidence intervals will be calculated.

For BVAS ver3, VDI, SF-36, and VAS, their changes over time will be presented using descriptive statistics (number of cases, mean value, standard deviation, minimum value, median value, and maximum value), and compared between the groups by the analysis of variance model.

Glucocorticoid dose changes over time will be presented using descriptive statistics for each group, and cumulated amounts will be compared between groups with Wilcoxon rank-sum test.

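### Survival, death, ESRD, time to first serious adverse event and the composite are tied to a FAS that can drop early treated deaths, and the serious adverse event proportion is assigned to two analysis sets with no rule for which is reported

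*Protocol*

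**What the plan says.** Section 9.2 lists under Efficacy "Overall survival period, relapse-free period, time to ESRD, time to the first serious adverse event" and, for 6 and 24 months, "The proportion of death, relapse, ESRD, or serious adverse events, and proportion of a composite outcome thereof" (relapse only at 24 months). Section 10.5.2.2 analyses these among the secondary efficacy endpoints: time-to-event and competing-risk methods for the first group, proportions with two-sided 95% intervals for the second.

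Section 10.5 assigns the sets. For efficacy: "In all efficacy assessments, the analysis in the full analysis set (FAS) is the primary analysis"; the PPS, a subset of the FAS, is for reference. For safety: "Safety Analysis Set will be used for safety-related analyses".

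To enter the FAS (10.1.1) a patient must have been dosed and have "visited hospital at least once during the treatment period, from which efficacy data are available". Patients without baseline data or with a serious protocol violation are removed. The safety set (10.1.3) asks only for one dose, and "The subjects are divided into groups according to the trial medication that they actually received".

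The Safety list in 9.2 names the SAE proportion again: "The number of occurrence and proportion of adverse events and serious adverse events that occurred (at 6 and 24 months". Section 10.5.2.3 compares it between groups by chi-square or Fisher's exact test. Neither that list nor 10.5.2.3 names death or survival separately. Death is the first criterion in the SAE definition (7.6.2).

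**The concern.** Whether a patient died, reached ESRD or had an SAE can be known without an efficacy visit. A set that requires one makes inclusion in a mortality analysis depend on having stayed well enough to be assessed, and the patients most exposed to exclusion are those who die or are harmed early. The condition arises after randomisation, in an open-label trial where sections 10.3 and 10.4 leave case and data handling to the coordinating investigator as a general rule.

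These endpoints matter to the trial's argument. Section 1.2 attributes about half of deaths in Japanese patients to infection, and the rationale in 9.2 says the composite is there to weigh efficacy against safety. If the two sets differ, the report would also carry two SAE proportions per arm for the same time point, from different patients and possibly different groupings, with no rule for choosing between them.

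**Working it through.** **1. The plan's own figure.** Section 10.2 gives 63 per arm, and 70 after 10% withdrawal. With remission 0.80 in both arms, margin 0.20, one-sided alpha 0.025 and power 0.80:

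n = (1.960 + 0.842)² × (0.80×0.20 + 0.80×0.20) / 0.20² = 7.85 × 0.32 / 0.04 = 62.8, so 63; and 63/0.90 = 70.

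The figures reproduce and this point does not change them. The 70 serves below only as an assumed number treated per arm.

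**2. The sections side by side.**

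| Endpoint | List in 9.2 | Analysed in | Set under 10.5 |
|---|---|---|---|
| Overall survival, time to ESRD, time to first SAE | Efficacy | 10.5.2.2 | FAS |
| Proportions of death, ESRD, composite | Efficacy | 10.5.2.2 | FAS |
| SAE proportion, 6 and 24 months | Efficacy | 10.5.2.2 (interval) | FAS |
| SAE proportion, 6 and 24 months | Safety | 10.5.2.3 (test) | Safety set, by treatment received |

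A dosed patient who dies before a qualifying visit is therefore in the safety set, and the death counts there as an SAE. The same patient can be missing from the first three rows. The fourth row does not show deaths as deaths.

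**3. When this could happen.** Section 7.2 schedules month 0 at day 1 ± 3 and the next assessment at day 30 ± 7, that is, from day 23. If the FAS needs a post-baseline assessment, deaths before about that time are exposed. If the month 0 visit is enough, the visit condition excludes very few; the baseline-data and violation exclusions still apply.

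**4. Size, for illustration only.** Assume 70 treated in an arm, d deaths, and e patients outside the FAS. The documents give neither d nor e.

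If every excluded patient died, the FAS death proportion is (d − e)/(70 − e):

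- d = 3: 3/70 = 4.3%; e = 1 gives 2/69 = 2.9%.
- d = 5: 5/70 = 7.1%; e = 1 gives 4/69 = 5.8%; e = 2 gives 3/68 = 4.4%.
- d = 7: 7/70 = 10.0%; e = 1 gives 6/69 = 8.7%; e = 2 gives 5/68 = 7.4%.

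If the excluded patient survived, it is d/(70 − e). With d = 5 and e = 1, 5/69 = 7.2%, a change of about 0.1 point.

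For SAEs, assume 20 of 70 patients with an event (28.6% in the safety set). If the excluded patients all died, the FAS gives 19/69 = 27.5% for one and 18/68 = 26.5% for two. With no exclusions and no difference in grouping, the two SAE rates are identical.

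**The case against.** The strongest reply is that few treated patients will fall outside the FAS. BVAS is scheduled at month 0, rituximab starts by day 7 and is given weekly, so treated patients attend hospital early. Section 7.2 includes confirmation of survival among the assessments, and since the protocol classes survival as efficacy, efficacy data in 10.1.1 could be read to include it. That stands as a reason to expect a small number. It does not remove the rule, which stays open to the narrower reading and keeps its other exclusions.

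It can also be said that the double SAE listing is deliberate: SAE is a component of the composite on the efficacy side, with an interval there and a test on the safety side. This explains the listing, but does not justify two sets for the same stand-alone proportion. Both analyses are secondary and unadjusted for multiplicity, so no confirmatory conclusion turns on the choice.

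Three stronger readings are tempting, and the protocol does not support them:

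- A reader might infer that treated deaths outside the FAS vanish from the trial. They do not: under 7.6.2 and 10.1.3 each counts as an SAE in the safety set, and a safety-set death table in the SAP would be compatible with 10.5.
- A reader might infer that every exclusion moves an arm by more than a percentage point. That needs the excluded patient to have died.
- A reader might assume that event and survival status is already known for everyone. Section 7.3 gives one assessment at discontinuation, and 8.1 ties adverse event observation to 4 weeks after the final dose, with longer follow-up only where possible.

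**Conclusion.** The point holds as a fault in the assignment of endpoints to sets. On the protocol's wording, a patient who is dosed and dies early could be left out of the survival, death-proportion and composite analyses, although counted as an SAE in the safety set. The SAE proportion at 6 and 24 months has two assigned sets and no rule for which is reported.

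The size is unknown and probably small. In the illustration, one excluded death out of 5 lowers an arm's death proportion by 1.3 points (7.1% to 5.8%), and one excluded survivor raises it by about 0.1 point. These figures rest on assumed counts of treated patients, deaths and exclusions. The primary endpoint, the sample size and the non-inferiority conclusion are untouched.

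This is not a detail simply left to the SAP: the protocol itself fixes both the classification and the set, and an SAP that made all treated patients primary for survival would conflict with the rule in 10.5.

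**What to change.** Amend section 10.5 as follows.

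- Analyse overall survival, death, ESRD, time to first SAE and the composite in all randomised patients with valid consent who received at least one dose, by allocated arm, whether or not efficacy or baseline data exist. Censor time-to-event endpoints at last known status.
- Report the stand-alone SAE proportion once, from the safety analysis set alongside the other adverse events, and show deaths there as well. Moving this single report to the allocated-arm set instead would split SAEs from the other adverse events, which stay grouped by treatment received.
- Keep the FAS for remission, relapse, BVAS, VDI, SF-36, VAS and glucocorticoid dose. Relapse-free survival counts death as an event in the 9.2 table, so name its set explicitly.

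The valid-consent condition keeps the exclusion that 10.1.1 already makes for missing consent. The cost is one more analysis population to define and describe. No new follow-up is required, because patients whose status is unknown after withdrawal are censored; the number of such patients per arm should be shown.

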#### 10.5.1 Subject background

Distribution and descriptive statistics of the subject background data in each analysis set will be calculated for each treatment arm. For nominal variables and ordinal variables, the frequency and proportion of categories will be shown for each arm. For continuous variables, descriptive statistics (number of cases, mean value, standard deviation, minimum value, median value, and maximum value) will be calculated for each group. In intergroup comparisons, Pearson's chi-square test will be used for nominal variables, unless cells with an expected frequency less than 5 accounts for 20% or more where Fisher's exact test will be used, Wilcoxon rank-sum test will be used for ordinal variables, and t test will be used for continuous variables. The significance level to be used is 5% (two-sided).

#### 10.5.2.2 Secondary efficacy endpoint analyses

The secondary efficacy endpoint data will be analyzed for the purpose of discussions that supplement the results from the primary analyses. The adjustment of multiplicity will not be performed in the analyses on the secondary efficacy endpoints. The significance level in the hypothesis test will be 5% (two-sided), and confidence intervals to be calculated are two-tailed 95% confidence intervals.

Among the secondary endpoints, duration of remission, overall survival, relapse-free survival, time to ESRD, and time to the first serious adverse event are measured from the time of randomization as the starting point, and survival time analysis and competing risk analysis will be performed on lengths of time to respective events.

For proportions of death, relapse, ESRD, and serious adverse events, and proportions of the composite outcome thereof, proportions of occurrence of events at each time point and two-tailed 95% confidence intervals will be calculated.

For BVAS ver3, VDI, SF-36, and VAS, their changes over time will be presented using descriptive statistics (number of cases, mean value, standard deviation, minimum value, median value, and maximum value), and compared between the groups by the analysis of variance model.

Glucocorticoid dose changes over time will be presented using descriptive statistics for each group, and cumulated amounts will be compared between groups with Wilcoxon rank-sum test.

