## 7.2 Clinical assessments and laboratory evaluations during the study period

During the study period, the following clinical assessment and laboratory evaluations are performed as specified for each evaluation time point (at 0, 1, 2, 4, 6, 9, 12, 18, and 24 months, and when a relapse is confirmed; \* 0 month = day  $1\pm 3$  days, 1 month = day  $30\pm 7$  days, 2 months = day  $60\pm 15$  days, 4 months = day  $120\pm 15$  days, 6 months = day  $180\pm 15$  days, 9 months = day  $270\pm 30$  days, 12 months = day  $360\pm 30$  days, 18 months = day  $540\pm 30$  days, 24 months = day  $720\pm 30$  days). During the maintenance treatment period (from month 6 to month 18), interval of hospital visits should not exceed 3 months at a maximum.

- · Confirmation of medication adherence
- · Confirmation of concomitant medications

• Presence or absence of additional treatment for ANCA-associated vasculitis not included in study protocol

- · Observation of adverse events
- Body weight
- Vital signs (blood pressure, pulse, body temperature)
- Blood tests:

<Blood cell count> Red blood cells, hemoglobin, platelets, white blood cells, differential leukocyte counts, number of B cells

<Serum biochemical examinations> Total protein, albumin, electrolytes [Na, K, Cl], BUN, serum creatinine level, CPK, total bilirubin level, AST, ALT, ALP, LDH, γ-GTP, CRP, Ig-G, Ig-A, Ig-M, C3, C4, complement titer, T-Cho, LDL-C, HDL-C, TG, blood glucose, HbA1c, and MPO-ANCA and PR3-ANCA measured by ELISA (or CLEIA, FEIA)

Note that MPO-ANCA and PR3-ANCA data at the time of screening can be used as substitutes for data at 0 months.

• Urinary examinations: General urine tests (glucose, protein, occult blood), urinary sediment, urinary creatinine

- BVAS ver3
- VDI (at 0, 6, 12, 18, and 24 months only)
- SF-36 (at 0, 6, 12, 18, and 24 months only)
- $\cdot$  VAS

• Bone density of the lumbar spine (at 0, 12, and 24 months; images taken during day 1–28 are acceptable as 0-month data.)

- Pregnancy test1)
- Confirmation of survival, ESRD, remission or relapse
- 1) A urine pregnancy test will be performed (hCG  $\geq$ 25 IU/L).

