#### 10.5.2.3 Secondary safety endpoint analyses

This study is a non-inferiority trial, in which adverse effects of glucocorticoids are expected to be reduced in the low-dose group. The adjustment of multiplicity will not be performed in the analyses on the secondary safety endpoints. The significance level in the hypothesis test will be 5% (two-sided), and confidence intervals to be calculated are two-tailed 95% confidence intervals.

The number of cases in which adverse events and serious adverse events occurred and proportions of those with and without occurrence, etc. are aggregated in a group-by-group manner, and Pearson's chi-square test will be used for intergroup comparisons (or Fisher's exact test, when cells with an expected frequency less than 5 account for 20% or more).

For occurrence of new-onset diabetes requiring treatment, hypertension, dyslipidemia, sleep disorder

requiring treatment, pathological fractures, and infections (intravenous or oral antibiotics are used), the number of cases and proportions of cases with and without occurrence in each group are determined, and Pearson's chi-square test will be used for intergroup comparisons (or Fisher's exact test, when cells with an expected frequency less than 5 account for 20% or more).

For bone density of the lumbar spine, the data will be aggregated using summary statistics for each group, and compared between the groups by the analysis of variance model.

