## **10.5.3 Exploratory analyses**

For eGFR, IgG, and B cell count, their changes over time will be described with summary statistics for each group, and compared between the groups by the analysis of variance model. eGFR values will be calculated with the MDRD equation [17] (to be corrected with the coefficient for Japanese), and patients receiving dialysis will be assumed to have eGFR =  $0 \text{ ml/min}/1.73\text{m}_2$ .

For B cells being depleted/recovered, MPO-/PR3-ANCA remaining positive/turning to negative, and prednisolone discontinuation/continuation, the number of cases and proportion will be determined for each group, and Pearson's chi-square test will be used for intergroup comparisons (or Fisher's exact test, when cells with an expected frequency less than 5 account for 20% or more).

For time to B cell recovery, an analysis of competing risks will be performed.

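### Continuous outcomes measured at month 0 are compared by analysis of variance with no baseline covariate, which gives up precision whether the response is the visit value or the change

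*Protocol*

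**What the plan says.** Three sections of the protocol fix the model for the continuous outcomes.

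- **10.5.2.2 (secondary efficacy):** "For BVAS ver3, VDI, SF-36, and VAS, their changes over time will be presented using descriptive statistics". The same sentence ends by listing the summary statistics and naming the test: "minimum value, median value, and maximum value), and compared between the groups by the analysis of variance model".
- **10.5.2.3 (secondary safety):** "For bone density of the lumbar spine, the data will be aggregated using summary statistics for each group"; the arms are then tested with the model named in 10.5.2.2.
- **10.5.3 (exploratory):** "For eGFR, IgG, and B cell count, their changes over time will be described with summary statistics for each group", with the same between-group model.

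No covariate is named in any of them. Section 10.5 presents these as the major methods and leaves further detail to the SAP, which is not at hand.

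Baseline values are scheduled. Section 7.2 requires BVAS, VAS and blood tests (including serum creatinine and IgG) as "specified for each evaluation time point (at 0, 1, 2, 4, 6, 9, 12, 18, and 24 months". It also requires "SF-36 (at 0, 6, 12, 18, and 24 months only") and "Bone density of the lumbar spine (at 0, 12, and 24 months"). Scans from days 1 to 28 count as the month-0 bone-density value. Section 9.2 sets the endpoint times: 6 and 24 months for BVAS, SF-36 and VAS, and 24 months for bone density.

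**The concern.** Where an outcome is measured before or at the start of treatment and again later, the early value usually predicts the later one. An analysis of follow-up values that omits it leaves that predictable variation in the error term, and a chance difference between arms at month 0 passes into the estimate. An analysis of change uses the baseline by subtraction, but over-corrects whenever the correlation is below 1.

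Bone density is where this matters most. Section 7.6.5 measures it to evaluate steroid-induced osteoporosis, and the rationale in 9.2 counts the glucocorticoid-related safety items among the main interests of the study. None of these outcomes was used to size the trial, so their power is whatever about 70 patients per arm provides. The protocol already accepts adjustment for the primary endpoint, in the sensitivity analysis in 10.5.2.1, but does not extend it to the continuous outcomes.

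**Working it through.** **1. The plan's own figure.** The only sample-size figure is for the primary endpoint (3.1 and 10.2): one-sided alpha 0.025, power 0.8, 80% remission in both arms, margin 0.2.

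n = (1.960 + 0.842)² × (0.8×0.2 + 0.8×0.2) / 0.2² = 7.85 × 0.32 / 0.04 = 62.8, so 63 per arm. Then 63 / 0.9 = 70 per arm, 140 in total. The stated figures reproduce. No continuous outcome enters them.

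**2. What the response variable is.**
- *Bone density:* 10.5.2.3 refers only to the data. Neither change nor baseline appears.
- *BVAS, SF-36, VAS, eGFR, IgG:* the text speaks of changes over time. This could mean change from baseline, or the course of the values by visit. The second reading has some support: 10.5.2.2 uses the same phrase for glucocorticoid dose, where it naturally means the dose course, and 9.2 defines the endpoints as assessments at 6 and 24 months. Neither fact settles it, so both readings are worked through.

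**3. Precision.** Let r be the baseline-to-follow-up correlation within arm. The protocol gives no value, so r is an assumption and is shown over a range. With n per arm and SD σ, the variance of the between-arm difference is:
- ANOVA on follow-up values: 2σ²/n
- ANOVA on change, with equal SDs at both times: 2(1−r) × 2σ²/n
- ANCOVA with baseline: (1−r²) × 2σ²/n

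The ratio of ANCOVA to follow-up ANOVA is therefore 1−r². Its ratio to change ANOVA is (1−r²)/[2(1−r)] = (1+r)/2. The power columns use n = 70, two-sided 5%, and a difference of (1.960 + 0.842) × √(2/70) = 0.474 SD, for which follow-up ANOVA has 80% power.

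| r | ANCOVA / follow-up ANOVA | ANCOVA / change ANOVA | Power, change ANOVA | Power, ANCOVA |
|---|---|---|---|---|
| 0.1 | 0.99 | 0.55 | 55.1% | 80.4% |
| 0.3 | 0.91 | 0.65 | 65.8% | 83.6% |
| 0.5 | 0.75 | 0.75 | 80.0% | 89.9% |
| 0.7 | 0.51 | 0.85 | 95.1% | 97.5% |
| 0.9 | 0.19 | 0.95 | >99.9% | >99.9% |

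Both ratios are below 1 for every r between 0 and 1.

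**4. Chance imbalance.** The month-0 difference between arms has standard error √(2/70) = 0.169 SD, so its 95% range is ±0.33 SD. At that limit, follow-up ANOVA carries r × 0.33 SD into the estimate: 0.17, 0.23 and 0.30 SD at r = 0.5, 0.7 and 0.9. Change ANOVA carries (1−r) × 0.33 SD in the opposite direction: 0.17, 0.10 and 0.03 SD.

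**The case against.** **Baseline may already be used.** If changes over time means change from baseline, baseline enters by subtraction. A repeated-measures ANOVA with month 0 as a level would also use it. This stands for BVAS, SF-36, VAS, eGFR and IgG. A reader might infer that the plan ignores baseline throughout, but the documents support that clearly only for bone density. The reading also decides the size: at r = 0.9 the ratio is 0.19 on one and 0.95 on the other.

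**Covariates belong in the SAP.** This stands in part. A missing covariate list would be no finding. The point rests on the model that three sections do name, which is not a baseline-adjusted one.

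**ANOVA is not wrong.** This stands. A reader might infer bias or an inflated type I error, but under randomisation the comparison is unbiased on average and its standard error already allows for chance imbalance. What is lost is precision, together with protection against the imbalance actually observed.

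**The gain is uneven.** This stands. With 80% remission assumed, and remission requiring BVAS 0 (or at most 1 in a restricted case), most 6-month BVAS values would sit near the floor and r may be low. The ratio (1+r)/2 also needs equal SDs, which is doubtful for BVAS. Minimisation on eGFR below or above 50 ml/min limits gross eGFR imbalance, though within-stratum variation stays in the error term.

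**These outcomes are not the main evidence of benefit.** This also stands. A reader might infer that the safety case depends on them. Most glucocorticoid harms in 10.5.2.3 are proportions tested by chi-square or Fisher's test, which this point does not touch.

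**Conclusion.** The point holds as a minor one. The protocol names analysis of variance without a baseline covariate for outcomes that all have a scheduled month-0 value, and leaves the response variable unclear for all but bone density. Under either reading, adjusting for baseline is at least as precise. The variance ratio is 0.75, 0.51 or 0.19 against follow-up values, and 0.75, 0.85 or 0.95 against change, at r = 0.5, 0.7 and 0.9.

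These figures rest on assumed correlations and, for the change comparison, on equal SDs. The gain is likely largest for bone density, SF-36, VAS and eGFR, and may be negligible for 6-month BVAS. The documents do not support a claim that the planned comparisons are invalid or that baseline is discarded for every outcome. Only secondary and exploratory analyses without multiplicity control are affected. The primary non-inferiority conclusion and the sample size are not.

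**What to change.** In 10.5.2.2, 10.5.2.3 and 10.5.3, replace analysis of variance by analysis of covariance with the month-0 value as covariate, at the endpoint times already stated (6 and/or 24 months), and state the response variable. The allocation factors may be added. A repeated-measures model is optional. VDI may keep a baseline-free comparison, since the note in Appendix 23.3 puts the score normally at 0 in the first three months of disease.

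Two details for bone density should be written down. The baseline scan may be taken up to day 28, shortly after treatment starts, and the text should say so. The bone-density analysis uses the safety set, which, unlike the FAS (10.1.1), does not require baseline data, so the handling of a missing month-0 scan should be stated.

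The cost is a change of analysis wording before data fixation. No new data, visits or patients are needed.
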